6.4. Covariates and Subgroups

The protocol does not define any formal subgroup analyses, and the study is not adequately powered to perform subgroup analyses.

6.5. Missing Data

All attempts will be made to collect all data per protocol. As missing data are expected to be minimal, no imputation will be performed for missing values [2]. Any data point that appears to be erroneous or inexplicable based on clinical judgment will be investigated as a possible outlier. If such data points are identified as scientifically valid outliers, sensitivity analyses will be performed to examine the impact of including or excluding the outliers. Any substantive differences in these analyses will be reported.

6.6. Interim Analyses and Data Monitoring

Interim analyses will only be used to terminate this trial in the event that unanticipated safety events deemed to be of sufficient concern require such action by the sponsor. These assessments will not be made on the basis of testing a formal statistical hypothesis; therefore, p-value adjustment will not be made to any analyses. A DSMB will be convened by DMID to review study progress and participant, clinical, safety, and reactogenicity and immunogenicity data.

An interim analysis will be performed after the 19 subjects enrolled in 2018 have completed the Day 113 visit. The interim analysis will include summaries of MN results for the M2SR-like H3N2 strain and both 2018-2019 QIV-like H3N2 strains as well as safety and reactogenicity data. This streamlined report will be made available to the sponsor for planning subsequent trials. These analyses will not be used to make any decisions concerning the conduct of this trial. At the time of these analyses it is anticipated that subjects will remain in long term safety and immunogenicity follow-up and that enrollment will resume in 2019, so the presentation of these data will be in a format that prevents inadvertent unblinding of the sponsor or clinical investigators to any individual subject's treatment assignment. When it is not possible to display the data by treatment arm and maintain the blind for the investigators and sponsor, such as the presence of extreme values or noteworthy AEs, a presentation by treatment arm will not be provided until after the long-term safety follow-up is complete. No hypothesis testing will be included in the interim analysis. Tables to be generated in the interim analysis are marked with an asterisk (*).

6.7. Multicenter Studies

This study is conducted at a single clinical site.

6.8. Multiple Comparisons/Multiplicity

This study was designed to obtain preliminary estimates of the safety and immune response of one dose of M2SR followed by a dose of licensed QIV in a pediatric population. The study was not designed to test any specific null hypothesis, and as such no adjustment for multiple comparisons will be performed.

7. STUDY SUBJECTS

7.1. Disposition of Subjects

Table 16 will present a summary of the reasons that subjects were screened but not enrolled. A listing of all subjects that received study product is provided in Listing 1.

The composition of analysis populations, including reasons for subject exclusion, by treatment arm, is presented in Table 13.

The disposition of subjects in the study will be tabulated by study group (Table 12). The table shows the total number of subjects screened, enrolled, received at least one dose, discontinued dosing or terminated from study follow-up and the number completing the study.

A flowchart showing the disposition of study subjects, adapted from the Consort Statement [1] will be included (Figure 1). This figure will present the number of subjects screened, enrolled, lost to follow-up, and analyzed, by treatment arm.

A listing of subjects who discontinued dosing or terminated from study follow-up and the reason will be included in Listing 2.

7.2. Protocol Deviations

A summary of subject-specific protocol deviations will be presented by the reason for the deviation, the deviation category, and treatment group for all subjects (Table 5). Major deviations will be reviewed for possible subject exclusion from the per protocol population including deviations affecting eligibility at baseline, product administration deviations, primary endpoint missing data, and deviations relating to prohibited medications. See Section 6.3.2 for per protocol exclusion definitions. All subject-specific protocol deviations and non-subject specific protocol deviations will be included in Appendix 3 as data listings (Listing 3 and Listing 4, respectively).

8. IMMUNOGENICITY EVALUATION

This study was not designed to test a specific null hypothesis, rather the objective was to obtain preliminary estimates of immune response to the M2SR vaccine alone and after subsequent receipt of licensed seasonal QIV. Immunogenicity data summaries and analysis for secondary endpoints will be presented for the ITT and PP populations.

Immune responses for the M2SR strain (A/Brisbane/10/2007 (H3N2)) will be summarized at each time point presented overall and stratified by study arm. Immune responses for each QIV strain (egg-based A/Singapore/INFIMH-16-0019/2016 and cell culture-propagated A/North Carolina/04/2016 and any additional strains specific to the 2019/2020 QIV vaccine) will be summarized at each time point presented by stratified by study arm for each season and H3N2 QIV response overall. Descriptive summary statistics will be provided for all assays, strains, and time points.

HAI and MN serum antibody titer summaries will include GMT, the proportion of subjects with a titer $\geq 1:40$, GMFR, and the proportion of subjects achieving seroconversion along with corresponding 95% confidence intervals for each measure. Exact (Blaker) confidence intervals will be presented for proportional endpoints [3]. Summaries of HAI and MN responses are presented in [Table 20](#), [Table 21](#), [Table 22](#), [Table 23](#), [Table 24](#), [Table 25](#), [Table 26](#), [Table 27](#), [Table 28](#), and [Table 29](#).

For nasal sIgA responses, the GMT with corresponding 95% CI visits strain-specific and relative sIgA (relative sIgA = strain-specific sIgA / total sIgA) results will be reported for the M2SR and QIV A/H3N2 strains. For post-baseline visits GMFR with corresponding 95% CI will also be calculated, as well as the proportion of subjects with ≥ 2 -fold and ≥ 4 -fold rise with corresponding 95% CI. Differences in GMT and GMFR between study groups will be presented at each time point. For QIV-like strains, differences will be calculated between overall response to the year-matched QIV strains. Summaries of nasal sIgA responses are presented in [Table 30](#), [Table 31](#), [Table 32](#), and [Table 33](#).

Summaries of the frequency of influenza H3 HA-specific (M2SR-like and QIV-like viruses) and conserved internal viral protein-specific IFN- γ producing T-cells will include the mean (or geometric mean if data are log-normally distributed) and corresponding 95% confidence interval as well as the median, minimum, and maximum values. Fold rise from baseline will be summarized by arithmetic or Williams mean [4] if data are approximately normally or log-normally distributed, respectively, or median if data are not approximately normally distributed by inspection. Differences in frequency between the study groups will be presented. Differences in QIV-like strains will be calculated based on results to the year-matched strain. Sum Test, as appropriate. Summaries of IFN- γ producing T cells are presented in [Table 34](#), [Table 35](#), [Table 36](#), and [Table 37](#).

Figures depicting the GMT (HAI, MN, sIgA) or frequency (IFN- γ producing T cells) for each strain and assay over time will be presented beginning with [Figure 2](#) and continuing through [Figure 13](#) (GMTs), and [Figure 14](#), [Figure 15](#), [Figure 16](#), and [Figure 17](#) (frequencies).

Reverse cumulative distribution (RCD) plots will be presented for each assay (HAI, MN, and sIgA) and strain generated with separate panels for each visit, and separate curves within each panel for each study arm and overall. HAI and MN antibody titers for the M2SR-like and QIV-like A/H3N2 strains are shown beginning with [Figure 18](#) and continuing through [Figure 29](#).

The spearman correlation and corresponding p-value between strains for each assay (HAI, MN, relative and specific sIgA, and IFN- γ T cell responses) will be calculated at each time point within each study arm and

overall. The correlations will be depicted in scatter plots as [Figure 30](#), [Figure 31](#), [Figure 32](#), [Figure 33](#), [Figure 34](#), and [Figure 35](#).

The spearman correlation and corresponding p-value between HAI and MN antibody titers for each strain (M2SR-like and QIV-like A/H3N2 (within and between strains)) will be calculated at each time point within each study arm and overall. The correlation will be depicted in scatter plots in [Figure 36](#) and [Figure 37](#). The spearman correlation of T cell responses between peptides tested will be presented for each strain as shown in [Figure 38](#) and [Figure 39](#).

The spearman correlation and corresponding p-value between HAI and MN antibody titers and relative and specific sIgA as well as between T cell responses and sIgA (relative and specific) will be calculated at each time point within each study arm and overall. The correlation will be depicted in scatter plots in [Figure 40](#), [Figure 41](#), [Figure 42](#), [Figure 43](#), [Figure 44](#), [Figure 45](#), [Figure 46](#), [Figure 47](#), [Figure 48](#), and [Figure 49](#).

Data listings of HAI and MN assay results, nasal sIgA assay results, and IFN- γ ELISpot assay results will be provided in [Listing 8](#), [Listing 9](#), and [Listing 10](#), respectively. Listings will be sorted by study group, subject ID, and visit.

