#### **11.4.3. Secondary Immunogenicity Data**

Summaries and analysis of secondary immunogenicity data will be presented for the mITT and PP populations.

Immune responses in terms of strain-specific (A/Brisbane/10/2007-like H3N2 (H3N2 M2SR)) present in QIV, HAI and neutralization antibody titers will be summarized by treatment arm at each time point. Analyses will include number and proportion of subjects with a titer  $\geq 1:40$ , number and proportion of subjects achieving seroconversion (defined as either a pre-vaccination titer  $< 1:10$  and a post-vaccination titer  $\geq 1:40$  or a pre-vaccination titer  $\geq 1:10$  and a minimum four-fold rise in post-vaccination y titer), Geometric Mean Titers (GMTs) and Geometric Mean Fold Rise (GMFR) along with corresponding 95% confidence intervals (CIs).

Strain specific nasal sIgA responses with and without normalization to total sIgA at baseline will be summarized as the GMT and GMFR with corresponding 95% CIs. Descriptive summaries of the frequency of influenza H3 HA-specific (H3 M2SR-like and QIV-like viruses) and conserved internal viral protein-specific IFN-gamma ELISPOT will be provided.

Plots such as reverse cumulative distributions or longitudinal presentations of GMTs will be presented. Regression models of immune response controlling for baseline titers may be considered.

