1. PREFACE

The Statistical Analysis Plan (SAP) for “A Phase I Trial to Evaluate the Safety and Immunogenicity of an Influenza Vaccination Strategy Including a H3N2 M2SR Prime followed by a Seasonal Quadrivalent Inactivated Vaccine Boost in a Pediatric Population 9-17 years old” (DMID Protocol 17-0012) describes and expands upon the statistical information presented in the protocol.

This document describes all planned analyses and provides reasons and justifications for these analyses. It also includes sample tables, listings, and figures planned for the final analyses. Regarding the final analyses and Clinical Study Report (CSR), this SAP follows the International Conference on Harmonisation of Technical Requirements for Registration of Pharmaceuticals for Human Use (ICH) Guidelines, as indicated in Topic E3 (Structure and Content of Clinical Study Reports), and more generally is consistent with Topic E8 (General Considerations for Clinical Trials) and Topic E9 (Statistical Principles for Clinical Trials). The structure and content of the SAP provides sufficient detail to meet the requirements identified by the FDA and ICH, while all work planned and reported for this SAP will follow internationally accepted guidelines published by the American Statistical Association and the Royal Statistical Society for statistical practice.

This document contains four sections: (1) a review of the study design, (2) general statistical considerations, (3) comprehensive statistical analysis methods for efficacy and safety outcomes, and (4) a list of proposed tables and figures. Within the table, figure, and listing mock-ups (Appendices 1, 2, and 3), references to CSR sections are included. Any deviation from this SAP will be described and justified in protocol amendments and/or in the CSR, as appropriate. The reader of this SAP is encouraged to also review the study protocol for details on conduct of the study and the operational aspects of clinical assessments.

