3.3. Study Definitions and Derived Variables

Medically significant wheezing is defined as wheezing on physical exam, signs of respiratory distress (tachypnea, retractions, or dyspnea), hypoxemia (O_2 saturation < 95%), or new bronchodilator prescription, or use of daily bronchodilator therapy (not on an “as needed “basis) from receipt of the first vaccination through 3 months after the first vaccination. Wheezing experienced after first vaccination through Visit 02 is considered a solicited event. Wheezing recorded after Visit 02 is considered an AESI. For all wheezing events the following will be recorded: whether wheezing is diffuse or localized, respiratory rate, oxygen saturation, medications associated with wheezing, and physician’s description on auscultation.

For laboratory and immunogenicity measures the baseline value will be defined as the last value obtained prior to the first vaccination/dose of study product.

Individual Hemagglutination inhibition (HAI) and neutralization results will be reported as a titer with values of 10×2^k , where $k=0, 1, 2$, etc. The lower limit of detection for the HAI and neutralization assays is 1:10; values below the limit of detection will be reported as ‘<10’. Values used in analysis will be imputed as one-half the limit of detection ($10/2 = 5$). For analysis, the geometric mean of repeated HAI or neutralization results will for each subject and visit will be computed and used as the response for all subsequent calculations.

Individual nasal sIgA results will be reported as a titer with values of 2^k where $k=0, 1, 2$, etc. The lower limit of detection for the nasal sIgA results is 2; values below the limit of detection will be reported as <2. Values used in analysis will be imputed as one-half the limit of detection ($2/2 = 1$). For analysis, the geometric mean of repeated sIgA results for each subject and visit will be computed and used as the response for all subsequent calculations. Relative (normalized) strain-specific sIgA results will be calculated by dividing the strain-specific value by total sIgA at each time point for each subject.

The lower limit of detection for the frequency of conserved internal viral protein-specific IFN- γ T cells per million peripheral blood mononuclear cells (PBMC) as measured by ELISPOT assay is 0.

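### SAP 8 contrasts the arms on nasal sIgA and ELISPOT without a baseline-adjusted model, which costs precision by an amount that depends on an unstated correlation

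*SAP*

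**What the plan says.** SAP 8 treats the assays differently.

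- **HAI and neutralization:** "HAI and MN serum antibody titer summaries will include GMT", together with fold rise, the proportion at or above 1:40 and seroconversion, each with an interval. These are per-arm summaries; no difference between arms is planned.
- **Nasal sIgA:** "Differences in GMT and GMFR between study groups will be presented at each time point". This covers both the post-dose level and the change from baseline.
- **IFN-γ ELISPOT:** "Differences in frequency between the study groups will be presented". Change from baseline is described per arm only: "Fold rise from baseline will be summarized by arithmetic or Williams mean", or by the median, depending on how the data look. A stray fragment about a sum test follows the contrast sentences, so the intended comparison is not fully readable.

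Baseline is available and defined. SAP 4.1 schedules swabs and PBMC on Day 1 before vaccination, and SAP 3.3 states: "For laboratory and immunogenicity measures the baseline value will be defined as the last value obtained prior to the first vaccination/dose of study product".

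Protocol 11.4.3 says: "Regression models of immune response controlling for baseline titers may be considered". The SAP does not take this up. Its preface states "This document describes all planned analyses and provides reasons and justifications for these analyses", yet no regression or ANCOVA appears in it. Section 6.4, which is headed for covariates as well as subgroups, names no covariate and says only that "The protocol does not define any formal subgroup analyses" and that the study is not powered for them. The shells for Tables 30 to 37 have no column for any between-arm difference.

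**The concern.** The study's stated aim is estimation with about 25 children per arm, so the width of the intervals largely determines what the secondary mucosal and cellular results can show. A level contrast makes no use of the Day 1 value. A fold-rise contrast uses it with the slope fixed at 1, which adds baseline noise when the correlation is modest. Regression on baseline estimates the slope. With enough subjects it is at least as precise as either raw contrast, apart from one degree of freedom.

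For sIgA there is also an ambiguity. On the log scale, and with the same subjects at both visits, the GMT and GMFR contrasts differ by exactly the chance gap between the arms at baseline. The SAP does not say which of the two answers the mucosal objective. For ELISPOT the only planned contrast is the level, so its baseline goes unused between arms.

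Because the protocol leaves adjustment optional and the SAP is silent, the choice could end up being made after the data are seen.

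**Working it through.** The documents give no precision or power figure for any GMT, GMFR or frequency contrast (SAP Table 4 concerns proportions), so there is no stated figure to reproduce.

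**Inputs from the documents:** 1:1 allocation (SAP 4.4.3); 25 per arm, or 22 after 10% dropout (SAP 5); 95% confidence (SAP 6.1).

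**Assumptions:** the correlation ρ between baseline and post-dose value is given nowhere, so it is taken as 0.3 to 0.7. Baseline and post-dose SDs are taken as equal. Contrasts are on the log scale.

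**Variance of the arm difference**, in units of 2·SD²/n:

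- post-dose level: 1
- fold rise: 2(1 − ρ)
- adjusted for baseline: 1 − ρ²

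Precision lost is 1 − Var(adjusted)/Var(unadjusted). This equals ρ² against the level and (1 − ρ)/2 against the fold rise.

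| ρ | Fold-rise variance | Adjusted variance | Loss vs level | Loss vs fold rise | Loss vs better of the two |
|---|---|---|---|---|---|
| 0.3 | 1.40 | 0.91 | 9% | 35% | 9% |
| 0.4 | 1.20 | 0.84 | 16% | 30% | 16% |
| 0.5 | 1.00 | 0.75 | 25% | 25% | 25% |
| 0.6 | 0.80 | 0.64 | 36% | 20% | 20% |
| 0.7 | 0.60 | 0.51 | 49% | 15% | 15% |

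The last column applies to sIgA, where both contrasts are planned. For ELISPOT only the level column applies.

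**Interval width against the better sIgA contrast:**

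- ρ = 0.3: √0.91 = 0.954, about 5% narrower
- ρ = 0.5: √0.75 = 0.866, about 13% narrower
- ρ = 0.7: √(0.51/0.60) = 0.922, about 8% narrower

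At ρ = 0.5 and 25 per arm, the half-width goes from 1.96·√(2/25) = 0.554 SD to 0.554 × 0.866 = 0.480 SD. At 22 per arm it goes from 0.591 to 0.512 SD. In sample-size terms, 50/0.75 ≈ 67 subjects analyzed unadjusted would match 50 analyzed with adjustment.

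**Cost of estimating the slope:** in 40,000 simulated trials at ρ = 0.5, the realized loss was 24% against the level and 23% against the fold rise, at both 25 and 22 per arm. At ρ = 0.3 the loss against the level was 7% to 8%.

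**Baseline gap:** its standard error is √(2/25) = 0.28 SD, or √(2/22) = 0.30 SD. The chance that the two sIgA contrasts differ by more than 0.3 SD is then about 29% at 25 per arm and 32% at 22.

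**The case against.** The strongest reply is that this is an exploratory Phase I study with no formal hypothesis, that GMT and GMFR are both named secondary endpoints, and that a baseline row is tabulated, so any imbalance will be visible. Much of this stands. GMT and GMFR contrasts follow from the endpoint definitions, and nothing requires their removal. But an estimation aim makes the precision of the estimate the issue, and a visible imbalance does not tell the reader which of two differing estimates to use.

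A reader might infer that a quarter of the precision is being thrown away. The documents do not support that as a fact. The figure needs ρ = 0.5, and under equal SDs it is the most that can be lost against the better sIgA contrast. A reader might also infer that baseline is ignored throughout. It is not: the sIgA fold-rise difference uses it, inefficiently. Analyzing sIgA relative to total sIgA is a further planned refinement, though it does not adjust for baseline.

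Two practical objections also stand. ELISPOT has a stated lower limit of 0, so a plain log model is undefined for zeros. And SAP 4.1 makes ELISPOT conditional, with its analysis deferred to an addendum, while SAP 3.2.2 and 8 list it as a secondary analysis, so whether it will be run is itself unclear.

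**Conclusion.** The point holds as a free gain in precision that the plan leaves unused. No between-arm immunogenicity contrast in SAP 8 comes from a baseline-adjusted model, and the option in the protocol is neither adopted nor declined.

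For ρ between 0.3 and 0.7 the loss is 9% to 49% for a level contrast, 35% to 15% for the sIgA fold-rise contrast, and 9% to 25% against the better of the two for sIgA. The loss against the level is ρ² whatever the SDs. The other two figures need equal SDs, and the 25% ceiling does not apply without them. Discrete sIgA titers, values below the detection limit and ELISPOT zeros make all of these figures approximate.

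It would be tempting to conclude that the results are biased or that a test loses power. Neither follows: under randomization both raw contrasts are unbiased, and no sIgA or ELISPOT test is clearly specified. Nor can it be said that the gates for exploratory assays in SAP 8.3 would open differently, since they rest on scientific judgment without a numerical threshold. The harm is limited to wider intervals and an unresolved choice between two sIgA estimates.

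**What to change.** In SAP 8, name one main between-arm estimate for sIgA at each post-baseline visit: a regression of log post-dose titer on arm and log baseline titer, reported as the adjusted geometric mean ratio with 95% CI. Apply it to the values with and without normalization. Keep the Day 1 value as baseline at every visit, as SAP 3.3 already defines, including after QIV. Retain the GMT and GMFR differences as supporting descriptive results.

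For ELISPOT, where performed, use the same model on a scale that allows zeros, such as log(x + 1), which is consistent with the Williams mean already planned. Complete or delete the sum-test fragment, and state whether ELISPOT is conditional.

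The cost is SAP wording, one model per table and visit, and one degree of freedom (47 residual instead of 48 at 25 per arm). Tables 30 to 37 need a column for the contrast in any case. No new data, p-values or multiplicity provisions are required.

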6. GENERAL STATISTICAL CONSIDERATIONS

6.1. General Principles

Unless otherwise specified, continuous variables will be summarized using the following descriptive statistics: n (non-missing sample size), mean, standard deviation, median, maximum and minimum. For post-baseline visits, fold rise from baseline will be calculated. Unless otherwise specified, confidence intervals for means (arithmetic or geometric) will be calculated using the student's t distribution with confidence level $\alpha=0.05$ (95% confidence). P-values for spearman correlations will be calculated using the student's t distribution testing the hypothesis that the two variables tested are not correlated. The frequency and percentages (based on the non-missing sample size) of observed levels will be reported for all categorical measures. In general, all data will be listed, sorted by site, study group and subject, and when appropriate by visit number within subject. All summary tables will be structured with a column for each study group in the order presented in [Table 1](#) and will be annotated with the total population size relevant to that table/treatment, including any missing observations.

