[Implementation Note: A generic sample figure is shown below. The scatter plots will be presented in a single figure with separate panels (rows) for each visit (baseline and 8, 22, 57, and 113 days post dose 1) and two columns (HAI and MN). M2SR-like antibody will be the X-axis; QIV-like antibody will be the Y-axis. Visit labels should be included in the panel header. Within each panel distinct marker types and colors should be used to indicate the study arms, with labels included in a legend. Use filled/unfilled markers to indicate the 2018/2019 versus 2019/2020 QIV strains. The spearman correlation should be calculated over all subjects and annotated within each panel as:

“Spearman Correlation:
All Subjects (r=0.xx, p=0.xx)
M2SR (r=0.xx, p=0.xx)
Placebo (r=0.xx, p=0.xx)”

This figure will be repeated for QIV strains with the HA Glycosylation Site retained (cell-based, A/North Carolina for 2018/2019, Turkey and Guinea pig RBC, with and without oseltamivir) and missing (egg-based, A/Singapore for 2018/2019).]

Figures with similar format:

Figure 31: Correlation of Serum Antibody Responses Against M2SR-like versus QIV-like H3N2 Viruses by Study Day and Study Group, PP Population

Figure 32: Correlation of Serum Antibody Responses Against QIV-like H3N2 Viruses by Study Day and Study Group, PP Population

[Implementation Note: The scatter plots will be presented in a single figure with separate panels (rows) for each visit (baseline and 8, 22, 57, and 113 days post dose 1) and two columns (HAI and MN). Egg-based strains (A/Singapore for 2018/2019 QIV) will be the X-axis, cell-based strains (A/North Carolina for 2018/2019 QIV) will be the Y-axis. Visit labels should be included in the panel header. Within each panel distinct marker types and colors should be used to indicate the study arms, with labels included in a legend.

Use filled/unfilled markers to indicate the 2018/2019 versus 2019/2020 QIV strains. The spearman correlation should be calculated over all subjects and annotated within each panel as:

“Spearman Correlation:

All Subjects ($r=0.xx$, $p=0.xx$)

M2SR ($r=0.xx$, $p=0.xx$)

Placebo ($r=0.xx$, $p=0.xx$)”

This figure will be repeated for A/North Carolina tested with Turkey and Guinea pig RBC, with and without oseltamivir]

- Figure 33: Correlation of Serum Antibody Responses Against QIV-like H3N2 Viruses by Study Day and Study Group, PP Population**

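### After dosing, the All Subjects Spearman r and p in the SAP correlation figures mix the arm effect with within-subject association and need an arm-stratified value; the Day 92 panel is also missing

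*SAP*

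**What the plan says.** SAP 8 sets out several families of Spearman correlation. One is "The spearman correlation and corresponding p-value between strains for each assay". Others pair HAI with MN, serum antibody with nasal sIgA, and T cell responses with sIgA. For these pairs the coefficient and p-value "will be calculated at each time point within each study arm and overall". The sentence on T cell responses between peptides mentions neither a p-value nor an overall value.

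The Figure 30 note in SAP Appendix 2 gives the layout: "The spearman correlation should be calculated over all subjects and annotated within each panel as" three lines, beginning "All Subjects (r=0.xx, p=0.xx" and "M2SR (r=0.xx, p=0.xx", with a matching Placebo line. Arms have distinct markers. The Figure 32 note repeats this, and the remaining correlation figures are listed as having a similar format. Panels are for "baseline and 8, 22, 57, and 113 days post dose 1".

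On the test, SAP 6.1 states: "P-values for spearman correlations will be calculated using the student's t distribution", with no correlation as the null hypothesis. SAP 6.8 makes no multiplicity adjustment because the study tests no specific null hypothesis. No table shell contains a correlation, so these figures are the only planned summary of them.

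**The concern.** The scientific question is whether a subject with a strong serum response also has a strong mucosal or T cell response, and whether a response to one strain carries over to another. That is a question about subjects within an arm. After the first vaccination one arm has had M2SR and the other saline. If M2SR raises both plotted measures, the scatter becomes two clusters, one displaced up and to the right, and the pooled coefficient is positive even when nothing is associated within either cluster. The All Subjects line is printed first and has twice the sample of either arm line. A reader could take a small p-value there as evidence that the responses track each other, when part or all of it is the treatment effect already reported in the arm-by-arm summaries.

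**Working it through.** The documents state no size, power or error rate for the correlations, so there is no planned figure to reproduce.

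**Inputs.** From SAP 5: 25 per arm, or 22 after 10% dropout. From SAP 4.4.3: 1:1 allocation. From SAP 6.1: p from the t distribution. Assumptions: two-sided 0.05 (no threshold is stated for correlations); no correlation within either arm; arm shifts d1 and d2, in within-arm SD, on the two measures.

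**Expected pooled coefficient.** With normal measures and equal arms, the mean scaled rank differs between arms by Φ(d/√2) − 0.5. The two measures then have rank covariance of one quarter of the product of those differences, and Spearman's rho is 12 times that:

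rho = 3 × [Φ(d1/√2) − 0.5] × [Φ(d2/√2) − 0.5]

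If either shift is zero, rho is zero. With d1 = d2 = d:

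- d = 0.5: 3 × 0.138² = 0.06
- d = 1.0: 3 × 0.260² = 0.20
- d = 1.5: 3 × 0.356² = 0.38
- d = 2.0: 3 × 0.421² = 0.53

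**Threshold for p<0.05.** |rho| must exceed t/√(t² + df). For 50 subjects this is 2.011/√(2.011² + 48) = 0.279; for 44 it is 2.018/√(2.018² + 42) = 0.297.

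**Rejection rate.** Simulation, 20,000 trials per setting:

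| Shift on both (SD) | Mean pooled rho | p<0.05, 25 per arm | p<0.05, 22 per arm |
|---|---|---|---|
| 0 | 0.00 | 5% | 5% |
| 0.5 | 0.06 | 7% | 6% |
| 0.75 | 0.12 | 13% | 13% |
| 1.0 | 0.20 | 30% | 26% |
| 1.25 | 0.29 | 55% | 50% |
| 1.5 | 0.38 | 81% | 75% |
| 2.0 | 0.53 | 99% | 98% |

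A 1.5 SD shift on one measure only leaves the rate at 5%.

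**Benchmark for the shift.** SAP Table 4 lists detectable differences in responder proportions. On a latent normal scale, 0.20 to 0.56 is Φ⁻¹(0.56) − Φ⁻¹(0.20) = 0.15 + 0.84 = 0.99 SD. The rows with comparator rates of 0.20 to 0.60 give 0.96 to 1.09 SD at N = 25 and 1.09 to 1.22 SD at N = 22. (The 0.80 row runs to a proportion of 1.0 and gives no usable shift.) If both measures shifted that much, the rate would be about 26% to 39% at N = 25 and from 35% to just under 50% at N = 22. These are differences the design could detect, not effects the sponsor predicts.

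**Two-fold titres.** Assuming placebo GMT about 20, a floor at 5 and log2 SD 1.5, GMT ratios of 2, 4 and 8 give 10%, 62% and 99% at 25 per arm (10%, 57% and 98% at 22). At ratio 4 and 25 per arm, log2 SDs of 1.25 and 2.0 give 86% and 29%.

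**Arm-adjusted alternative.** Rank over all subjects, centre the ranks within arm, correlate, and use 2n − 3 degrees of freedom for n per arm. The rate is 4.7% to 5.4% at every shift tried. The single-arm correlations already planned hold 4.8% to 5.5%. With a true within-arm correlation of 0.3 and 25 per arm, the adjusted version reaches p<0.05 about 51% of the time, against 28% for one arm alone.

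**Day 92.** SAP 4.1 schedules serum, nasal and PBMC sampling immediately before QIV at Day 92, the Table 20 shell has a Day 92 block, and SAP 8 covers each time point. The Figure 30 and 32 notes list baseline and Days 8, 22, 57 and 113 only.

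**The case against.** The strongest reply is that the plan already supplies the remedy. Each arm's r and p are printed in the same panel, with separate markers, so in the scenario above a reader would see two clusters and two near-zero coefficients beside the pooled value. That stands, and it limits the harm.

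Second, the pooled p-value is not a false positive for the hypothesis in SAP 6.1: if the vaccine raises both measures, they are correlated across all subjects. This is formally right. But the marginal correlation then partly restates an arm contrast that the GMT, fold-rise and responder summaries already show, and it does not answer whether responses track each other within subjects.

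Third, the shifts are assumptions, and zero within-arm correlation is the extreme case. It is least natural for two H3N2 strains measured by the same assay on the same sample. This also stands: where real within-arm association exists, the pooled value adds the arm effect to it.

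Fourth, the study is exploratory, correlations are not among the endpoints, and the exploratory assays in SAP 8.3 depend on response increases in the M2SR arm, not on correlations. This stands in full.

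A reader might infer that the plan will report significant correlations where none exist, or that it offers only the pooled figure. The documents support neither: inflation depends on an effect on both measures whose size they do not state, and the arm-specific results are required.

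**Conclusion.** The point holds as a modest improvement. The All Subjects r and p at post-dose visits combine the arm effect with within-subject association and overstate the latter whenever M2SR raises both measures. The size depends on the unknown shift: negligible at 0.5 SD (6% to 7%), 26% to 30% at 1.0 SD, and 75% or more from 1.5 SD, assuming no within-arm correlation and 22 to 25 per arm. Baseline panels are unaffected, as are pairs in which only one measure responds. At Day 113 both arms have had QIV, so only a priming difference can produce it. The documents do not support the further inference that every small pooled p-value is spurious or that a trial decision is at risk. The missing Day 92 panel is a separate, plain mismatch between SAP 8 and the figure notes.

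**What to change.** In SAP 8 and the correlation figure notes, for post-dose visits, replace the All Subjects coefficient and p-value with a Spearman correlation stratified by arm (partial Spearman given arm). If the pooled value is kept, print the stratified value beside it and label the pooled one as unadjusted for arm. Keep the M2SR and Placebo lines, and leave the baseline panel as planned. Separately, add Day 92 to the visit rows in the Figure 30 and 32 notes and in the figures that follow their format. The cost is a few lines of programming and SAP wording, with no new samples or data. The gain is a full-sample correlation free of the arm effect, with more power for a true within-arm association than either arm alone.
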